**CONFIDENTIAL**

**Appendix A Schedule of Study Procedures (continued)**

Study Day	Screening/ Baseline Period (a)	Part 1: Double-Blind Treatment Period (b)			Part 2: Open-Label Treatment Period (b)			Follow-up Period (c)	
	Days -41 to 0	Day 1	Day 11	Day 21	Day 31	Day 41	Day 85 (c,d)	Day 91	Day 121
Visit Window (days)			±2	±2	±2	±2	±2	±2	±2
Visit Number	1 Screening Visit	2	3	4	5	6	7 Final Visit	8 Follow-up Phone Call	9 Follow-up Visit
Neurological exam, including funduscopy and visual acuity (if possible) (k)	X			X			X		
12-lead ECG	X	X			X		X		
Clinical laboratory tests (l)	X	X			X		X		
CCI									
CCI									
Plasma sample for TAK-935 PK (m,n)		X	X	X	X	X	X		
Plasma sample for AED analysis (n,o)		X	X	X	X	X	X		X
Plasma sample for PD (n,p)	X	X	X	X	X	X	X		X
Blood sample for DNA PGx (q)		X							
Blood sample for RNA PGx (n,r)		X			X				
Access IVRS/IWRS for subject ID/medication ID/subject status (s)	X	X	X	X	X	X	X		
Assess benefit-risk analysis with subject and caregiver before increasing dose to 300 mg BID				X					
Dispense study drug with dosing card (t)		X	X	X	X	X	X		
In-clinic administration of morning dose of study drug (u)		X	X	X	X	X	X		

(Footnotes follow table.)

**CONFIDENTIAL**

**Appendix A Schedule of Study Procedures (continued)**

	Screening/ Baseline Period (a)	Part 1: Double-Blind Treatment Period (b)			Part 2: Open-Label Treatment Period (b)			Follow-up Period (c)	
Study Day	Days -41 to 0	Day 1	Day 11	Day 21	Day 31	Day 41	Day 85 (c,d)	Day 91	Day 121
Visit Window (days)			±2	±2	±2	±2	±2	±2	±2
Visit Number	1 Screening Visit	2	3	4	5	6	7 Final Visit	8 Follow-up Phone Call	9 Follow-up Visit
Study drug return/ accountability/compliance			X	X	X	X	X		X
Assess AEs (v)	X	X	X	X	X	X	X	X	X

**Footnotes for Appendix A**

(a) The 4-week baseline seizure diary recording can begin as soon as the ICF has been signed. Randomization can occur once the 4-week baseline seizure count of  $\geq 1$  has been obtained and the subject meets all of the inclusion and none of the exclusion criteria.

(b) Three days after each dose up-titration or de-escalation, subjects will be contacted by phone to monitor study drug compliance, concomitant medication use, and AEs.

(c) Subjects who do not enter Part 2 or withdraw early from the study should complete all procedures scheduled for the Final Visit (Visit 7) at time of withdrawal, including dose de-escalation as appropriate, followed by the Follow-up Period (Visits 8 and 9). See Section 6.1 for details.

(d) Dose de-escalation, as appropriate, begins at the Final Visit (ie, if at TAK-935 300 mg BID level, reduce to 200 mg BID for 3 days followed by 100 mg BID for 3 days; if at the 200 mg BID level, reduce to 100 mg BID for 3 days; if at the 100 mg BID level, there is no de-escalation). See Section 6.1 for details.

(e) If urine cannot be collected, the reason should be documented in the source document.

(f) Subjects who are positive for hepatitis C Ab should return to the clinic for an unscheduled visit to provide a blood sample for HCV qPCR.

(g) If the subject is unable to comply with the C-SSRS due to developmental status, a parent proxy may be used for the completion of the C-SSRS. The investigator may also use clinical judgment to assess for suicidal ideation and behavior.

(h) For female subjects only at the Screening and Final Visits.

(i) For female subjects of childbearing potential, a serum pregnancy (hCG) test will be performed at the Screening and Final Visits and a urine pregnancy test will be performed before the morning dose on Day 1 in Part 1 (Visit 2). If urine cannot be collected, the reason should be documented in the source document and the serum pregnancy test obtained at Visit 1 must be confirmed to be negative by the investigator prior to randomization. Additional pregnancy tests may be performed throughout the study at the investigator's discretion.

(j) PE must be captured in the source document. Any clinically significant abnormalities noted prior to administration of study drug should be described and captured on the Medical History form. Any clinically significant changes in PE noted after administration of study drug should be captured on the AE page of the eCRF.

(k) Any clinically significant abnormalities noted prior to administration of study drug should be described and recorded on the Medical History form. Any clinically significant changes in the neurological examination noted after administration of study drug should be captured on the AE page of the eCRF.

(l) Hematology, serum chemistry, and urinalysis tests. If urine cannot be collected due to the subject's cooperation or because the subject is wearing a diaper, it is acceptable for the subject to continue in the study and the reason should be documented in the source document.

(m) PK plasma samples for measurement of TAK-935 and M-I concentrations will be collected before and 1, 3, and 5 hours after the morning dose on Day 1; before and approximately 1 hour after the morning dose on Days 11 and 21; and before the morning dose on Days 31, 41, and 85.

(n) On Days 11, 21, 31, 41, and 85, subjects should visit the clinic in the morning prior to taking their morning dose. For subjects who are not able to come for the visit during the

**CONFIDENTIAL**

morning hours, they should be instructed to take their morning dose, as usual, and come to the study site during the afternoon hours, as feasible for the subject. While in the clinic, the site should attempt to obtain 2 PK samples, separated by 1-2 hours, if possible. Hours since the last dose of the study medication must be recorded in the eCRF upon collection of the PK sample(s).

(o) Plasma samples for measurement of concomitant AED concentrations will be collected before the morning dose on Days 1, 11, 21, 31, 41, and 85; and at the Follow-up Visit (Day 121).

CCI

(q) One PGx blood sample for DNA isolation will be collected before the morning dose on Day 1.

(r) Two PGx blood samples for RNA isolation will be collected before the morning dose on Days 1 and 31.

(s) The dose of IP will be increased on Days 11 and 21 in Part 1 and on Day 41 in Part 2, provided there are no safety or tolerability concerns. Subjects' dose may be increased or decreased before Day 41 (Visit 6) based on clinical condition (ie, increasing seizures) and investigator judgment. At the end of Part 2, the dose of TAK-935 will be de-escalated before dosing is discontinued. See Section 6.1 for details.

(t) A dosing card will be provided to record daily AM and PM study drug administration throughout the study, including changes in dosing regimen (de-escalation) that may occur between visits and during the de-escalation period of the study.

(u) On in-clinic dosing days, after administration of study drug, appropriate mouth and/or hand checks will be performed to ensure that the dose is swallowed and noted in the source document. If a site visit is not possible during the morning hours, the subject should take their morning dose prior to attending the visit during the afternoon hours. The date and time of each dose will be recorded in the source documents and on the eCRFs.

(v) Collection of AEs will commence from the time informed consent is provided (Screening Visit) and continue until screen failure or the Follow-up Visit.

## Appendix B Responsibilities of the Investigator

Clinical research studies sponsored by the sponsor are subject to ICH GCP and all the applicable local laws and regulations. The responsibilities imposed on investigators by the FDA are summarized in the “Statement of Investigator” (Form FDA 1572), which must be completed and signed before the investigator may participate in this study.

The investigator agrees to assume the following responsibilities by signing a Form FDA 1572:

1. Conduct the study in accordance with the protocol.
2. Personally conduct or supervise the staff who will assist in the protocol.
3. If the investigator/institution retains the services of any individual or party to perform trial-related duties and functions, the investigator/institution should ensure that this individual or party is qualified to perform those trial-related duties and functions and should implement procedures to ensure the integrity of the trial-related duties and functions performed and any data generated.
4. Ensure that study-related procedures, including study-specific (nonroutine/nonstandard panel) screening assessments are NOT performed on potential subjects, prior to the receipt of written approval from relevant governing bodies/authorities.
5. Ensure that all colleagues and employees assisting in the conduct of the study are informed of these obligations.
6. Secure prior approval of the study and any changes by an appropriate IRB/IEC that conform to 21 Code of Federal Regulations (CFR) Part 56, ICH, and local regulatory requirements.
7. Ensure that the IRB/IEC will be responsible for initial review, continuing review, and approval of the protocol. Promptly report to the IRB/IEC all changes in research activity and all anticipated risks to subjects. Make at least yearly reports on the progress of the study to the IRB/IEC, and issue a final report within 3 months of study completion.
8. Ensure that requirements for informed consent, as outlined in 21 CFR Part 50, ICH, and local regulations, are met.
9. Obtain valid informed consent from each subject who participates in the study, and document the date of consent in the subject’s medical chart. Valid informed consent is the most current version approved by the IRB/IEC. Each informed consent form should contain a subject authorization section that describes the uses and disclosures of a subject’s personal information (including personal health information) that will take place in connection with the study. If an informed consent form does not include such a subject authorization, then the investigator must obtain a separate subject authorization form from each subject or the subject’s legally acceptable representative.
10. Prepare and maintain adequate case histories of all persons entered into the study, including eCRFs, hospital records, laboratory results, etc, and maintain these data for a minimum of 2 years following notification by the sponsor that all investigations have been discontinued or

that the regulatory authority has approved the marketing application. The investigator should contact and receive written approval from the sponsor before disposing of any such documents.

11. Allow possible inspection and copying by the regulatory authority of GCP-specified essential documents.
12. Maintain current records of the receipt, administration, and disposition of sponsor-supplied drugs, and return all unused sponsor-supplied drugs to the sponsor.
13. Report adverse reactions to the sponsor promptly. In the event of an SAE, notify the sponsor within 24 hours.

### **Appendix C Elements of the Subject Informed Consent**

In seeking informed consent, the following information shall be provided to each subject:

1. A statement that the study involves research.
2. An explanation of the purposes of the research.
3. The expected duration of the subject's participation.
4. A description of the procedures to be followed, including invasive procedures.
5. The identification of any procedures that are experimental.
6. The estimated number of subjects involved in the study.
7. A description of the subject's responsibilities.
8. A description of the conduct of the study.
9. A statement describing the treatment(s) and the probability for random assignment to each treatment.
10. A description of the possible side effects of the treatment that the subject may receive.
11. A description of any reasonably foreseeable risks or discomforts to the subject and, when applicable, to an embryo, fetus, or nursing infant.
12. A description of any benefits to the subject or to others that reasonably may be expected from the research. When there is no intended clinical benefit to the subject, the subject should be made aware of this.
13. Disclosures of appropriate alternative procedures or courses of treatment, if any, that might be advantageous to the subject and their important potential risks and benefits.
14. A statement describing the extent to which confidentiality of records identifying the subject will be maintained, and a note of the possibility that regulatory agencies, auditor(s), IRB/IEC, and the monitor may inspect the records. By signing a written informed consent form, the subject or the subject's legally acceptable representative is authorizing such access.
15. For research involving more than minimal risk, an explanation as to whether any compensation and an explanation as to whether any medical treatments are available if injury occurs and, if so, what they consist of or where further information may be obtained.
16. The anticipated prorated payment(s), if any, to the subject for participating in the study.
17. The anticipated expenses, if any, to the subject for participating in the study.
18. An explanation of whom to contact for answers to pertinent questions about the research (investigator), subject's rights, and IRB/IEC and whom to contact in the event of a research-related injury to the subject.

19. A statement that participation is voluntary, that refusal to participate will involve no penalty or loss of benefits to which the subject otherwise is entitled, and that the subject or the subject's legally acceptable representative may discontinue participation at any time without penalty or loss of benefits to which the subject is otherwise entitled.
20. The consequences of a subject's decision to withdraw from the research and procedures for orderly termination of participation by the subject.
21. A statement that the subject or the subject's legally acceptable representative will be informed in a timely manner if information becomes available that may be relevant to the subject's willingness to continue participation in the study.
22. A statement that results of PGx analysis will not be disclosed to an individual, unless prevailing laws require the sponsor to do so.
23. The foreseeable circumstances or reasons under which the subject's participation in the study may be terminated.
24. A written subject authorization (either contained within the informed consent form or provided as a separate document) describing to the subject the contemplated and permissible uses and disclosures of the subject's personal information (including personal health information) for purposes of conducting the study. The subject authorization must contain the following statements regarding the uses and disclosures of the subject's personal information:
  - a) that personal information (including personal health information) may be processed by or transferred to other parties in other countries for clinical research and safety reporting purposes, including, without limitation, to the following: (1) Takeda, its affiliates, and licensing partners; (2) business partners assisting Takeda, its affiliates, and licensing partners; (3) regulatory agencies and other health authorities; and (4) IRBs/IECs;
  - b) it is possible that personal information (including personal health information) may be processed and transferred to countries that do not have data protection laws that offer subjects the same level of protection as the data protection laws within this country; however, Takeda will make every effort to keep your personal information confidential, and your name will not be disclosed outside the clinic unless required by law;
  - c) that personal information (including personal health information) may be added to Takeda's research databases for purposes of developing a better understanding of the safety and effectiveness of the study drug(s), studying other therapies for patients, developing a better understanding of disease, and improving the efficiency of future clinical studies;
  - d) that subjects agree not to restrict the use and disclosure of their personal information (including personal health information) upon withdrawal from the study to the extent that the restricted use or disclosure of such information may impact the scientific integrity of the research; and

- e) that the subject's identity will remain confidential in the event that study results are published.
25. Female subjects of childbearing potential (eg, nonsterilized, premenopausal female subjects) who are sexually active must use highly effective contraception (as defined in the informed consent) from Screening throughout the duration of the study, and for 30 days after last dose. Regular pregnancy tests will be performed throughout the study for all female subjects of childbearing potential. If a subject is found to be pregnant during study, study drug will be discontinued and the investigator will offer the subject the choice to receive unblinded treatment information.
  26. Male subjects must use highly effective contraception (as defined in the informed consent) from signing the informed consent throughout the duration of the study, and for 30 days after last dose. If the partner or wife of the subject is found to be pregnant during the study, the investigator will offer the subject the choice to receive unblinded treatment information.
  27. A statement that clinical trial information from this trial will be publicly disclosed in a publicly accessible website, such as [ClinicalTrials.gov](http://ClinicalTrials.gov).

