**Table 9.a Approximate Blood Volume**

Sample Type	Sample Volume (mL)	Number of Samples (a)			Total Volume (mL)
		Screening Visit	Part 1	Part 2	
HIV, HBsAg, HCV (b)	6	1	---	---	6
HCV RNA detection by qPCR (c)	6	1	---	---	6
FSH (d)	(d)	1		1	(d)
Estradiol (e)	2	1		1	4
Serum chemistry (f)	6	1	1	2	24
Hematology	2	1	1	2	8
Plasma sample for TAK-935 PK analysis	4	---	8	3	44
Plasma sample for AED analysis	4	---	3	3	28
Plasma sample for PD analysis (g)	4	2	16	6	104
Blood sample for DNA PGx	6	---	1	---	6
Blood sample for RNA PGx (g)	2.5	---	2	2	10
Total Blood Volume (mL)					240

--- =not applicable.

(a) Does not include blood draws at any unscheduled visits.

(b) One 2-mL blood sample for each test.

(c) Subjects who are positive for hepatitis C Ab should return to the clinic for an unscheduled visit to provide a blood sample for HCV qPCR.

(d) For diagnostic purposes in female subjects only; sample will be run from serum chemistry volume (no extra volume required).

(e) In female subjects only.

(f) Includes serum pregnancy test for female subjects of childbearing potential.

(g) Two blood samples per scheduled time.

The clinical laboratory tests to be performed are listed in [Table 9.b](#).

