**Abstinence:**

- Sexual abstinence, if it is the preferred and usual lifestyle of the subject, will be considered an acceptable method of contraception on a case-by-case basis upon prior approval by the Medical Monitor. Subjects practicing abstinence as a method of contraception must refrain from heterosexual intercourse throughout the duration of the study and for 30 days after last dose of study drug.

Subjects will be provided with information on acceptable methods of contraception as part of the subject informed consent process and will be asked to sign a consent form stating that they understand the requirements for avoidance of pregnancy, donation of ova, and sperm donation during the course of the study and for 30 days after the last dose of study drug. This may be signed by the legal representative of the subject.

All female subjects of childbearing potential must have a negative serum hCG pregnancy test at Screening (Visit 1) and a negative urine hCG pregnancy test on Day 1 (Visit 2), before receiving any dose of study drug. During the course of the study, subjects will receive continued guidance with respect to the avoidance of pregnancy and sperm donation as part of the study procedures. An additional serum hCG pregnancy test will be performed at the Final Visit.

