**9.1.13 Pregnancy**

If any subject is found to be pregnant during the study, she should be withdrawn and any sponsor-supplied drug should be immediately discontinued. In addition, any pregnancies in the partner of a male subject during the study or for 30 days after the last dose should also be recorded following authorization from the subject's partner.

If the pregnancy occurs during administration of active study drug, for example, after Visit 2 or within 30 days of the last dose of active study drug, the pregnancy should be reported immediately, using a pregnancy notification form, to the contact listed in Section 1.1.

Should the pregnancy occur during or after administration of blinded study drug, the investigator must inform the subject of their right to receive treatment information. If the subject chooses to receive unblinded treatment information, the individual blind should be broken by the investigator. Subjects randomized to placebo need not be followed.

If the female subject and/or female partner of a male subject agrees to the primary care physician being informed, the investigator should notify the primary care physician that the subject/female partner of the subject was participating in a clinical study at the time she became pregnant and provide details of treatment the subject received (blinded or unblinded, as applicable).

All reported pregnancies, including those in female partners of male subjects, will be followed up to final outcome, using the pregnancy form. The outcome, including any premature termination, must be reported to the sponsor. An evaluation after the birth of the child will also be conducted.

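### Required consent content promises regular pregnancy testing throughout the study, but a completer has only one scheduled test after dosing starts, at Day 85

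*Protocol*

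**What the plan says.** Protocol Appendix C opens with a binding instruction: "In seeking informed consent, the following information shall be provided to each subject". Item 25 of that list tells women of childbearing potential: "Regular pregnancy tests will be performed throughout the study for all female subjects of childbearing potential".

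The operational sections are narrower:

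- **Appendix A, pregnancy test row:** marked at Screening (serum), Day 1 (urine) and Day 85 (serum). Days 11, 21, 31, 41, 91 and 121 are blank.
- **Appendix A, footnote (i):** "a serum pregnancy (hCG) test will be performed at the Screening and Final Visits", with a urine test before the Day 1 morning dose. Beyond that, "Additional pregnancy tests may be performed throughout the study", at the investigator's discretion.
- **Section 9.1.12:** after the Screening and Day 1 tests, "An additional serum hCG pregnancy test will be performed at the Final Visit". Table 9.b footnote (f) says the same.
- **Section 9.1.13:** "If any subject is found to be pregnant during the study, she should be withdrawn", and study drug is to be stopped at once.

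Subjects who leave early or do not enter Part 2 have the Final Visit procedures, including the serum test, when they leave (Section 9.3.5 and Appendix A footnote (c)).

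**The concern.** Item 25 is unconditional: tests will be done, regularly, over the whole study, for every woman of childbearing potential. Two of the three scheduled tests come before the first dose. The only one after dosing starts comes at the end of treatment, and a test that may be done at discretion is not one that will be done for all.

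Two things are at stake. First, subjects, or the representatives who consent for them, may be told of more monitoring than the schedule provides. Second, the stopping rule in Section 9.1.13 works only once a pregnancy is known. Between Day 1 and Day 85 no scheduled test would reveal one, so detection depends on symptoms, on what emerges from counseling at visits, and on the investigator choosing to test.

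**Working it through.** The plan gives no figure of its own here, so the check counts scheduled tests and subtracts days.

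**Inputs**

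- Test days: Screening, Day 1 predose, Day 85 (Appendix A and footnote (i)).
- Visit window: ±2 days from Day 11 onward (Appendix A).
- Active dosing before Day 85: Days 1–84 in the TAK-935 arm; Days 31–84 for placebo subjects entering Part 2 (Section 6.1).
- Contraceptive failure: at most 1% per year with consistent, correct use (Section 9.1.12).
- Number of women of childbearing potential: not stated. Assumed 5, 10 or 20 of the roughly 20 subjects; 20 is an upper bound.

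**Count for a completer**

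Three scheduled tests, of which 2 are before dosing and 1 is after dosing starts.

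**Gap between tests**

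| Interval | Nominal days | With ±2-day windows |
|---|---|---|
| Day 1 to Day 85, as planned | 85 − 1 = 84 | 83 − 1 = 82 to 87 − 1 = 86 |
| Day 1 to Day 31, if a test is added | 31 − 1 = 30 | 29 − 1 = 28 to 33 − 1 = 32 |
| Day 31 to Day 85, if a test is added | 85 − 31 = 54 | 83 − 33 = 50 to 87 − 29 = 58 |

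If urine cannot be obtained on Day 1, footnote (i) falls back on the Screening serum result. With Screening as early as Day −41, the gap becomes 85 − (−41) = 126 days, or 18 weeks.

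**Active drug before the Day 85 test, worst case for a completer**

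- TAK-935 arm: 84 days.
- Placebo subjects entering Part 2: 84 − 31 + 1 = 54 days.

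**Expected pregnancies over 84 days**

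n × 0.01 × 84/365 = n × 0.0023

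- n = 5: 0.012
- n = 10: 0.023
- n = 20: 0.046

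These rise if contraception is not used consistently.

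**Provisions that might be read as further tests**

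- Table 9.a footnote (f), on serum chemistry: "Includes serum pregnancy test for female subjects of childbearing potential". This is a blood-volume note. It could suggest a test at every chemistry draw, but footnote (i) of Appendix A confines serum tests to two visits.
- SAP Table 7.a gives a Visit 3 window of Days 2–43 in the column that includes the pregnancy test. An analysis window assigns results to visits and does not schedule a test.

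**The case against.** The strongest reply is that item 25 speaks of the study and not of the treatment period. The study runs from consent, so three tests (at entry, before the first dose and at the end) are done for every woman of childbearing potential. Only the word regular remains in dispute, and the protocol attaches no interval to it. The consent form itself is not in the documents, and Appendix C item 4 requires a description of procedures, which could list the true test days. Pregnancy avoidance counseling is marked at every visit from Screening to Day 91, phone contacts follow dose changes, contraception is required of sexually active women, and discretionary tests are allowed. The expected number of pregnancies is a small fraction of one. A Day 31 test would still leave a 54-day gap, so it is a preference that no rule in the protocol requires.

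Part of this stands. The risk is low, the term is undefined, the form is unseen, and rewording alone would cure the inconsistency. But counting the two predose tests does not turn a single later test, 84 days on, into regular testing. Counseling and phone calls do not test for pregnancy. The lack of a definition is itself a reason to state the days. The extra test has to be justified as a cheap improvement, and on that footing it is worth making.

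**Conclusion.** The mismatch is real. The required consent content describes regular testing for all women of childbearing potential; the schedule gives a completer one test after dosing starts and an 84-day gap (82 to 86 with the window). The day counts follow directly from Appendix A. The expected pregnancy count (0.012 to 0.046) rests on an assumed 5 to 20 women and on the 1% annual ceiling holding in practice.

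This is a modest point about consent accuracy and early detection. It concerns the content the protocol requires, since the signed form cannot be checked, and it affects no endpoint or analysis.

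**What to change.** 1. **Add serum hCG on Day 31** for women of childbearing potential, in the Appendix A row, footnote (i) and Section 9.1.12. Clinical laboratory tests are already marked that day, and Table 9.a footnote (f) already counts the serum pregnancy test within the chemistry volume. The longest scheduled on-treatment gap falls from 84 to 54 days.
2. **Reword Appendix C item 25** to name the test days and to say that further tests are at the investigator's discretion. This is needed with or without the added test, and suffices to remove the mismatch if the sponsor declines step 1.

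Cost: one hCG assay per woman of childbearing potential, one mark in the schedule with its matching text, and one reworded consent element. No new visit and no extra blood.

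A Day 121 test is optional. It would need urine or a small extra serum sample. It would fall 121 − 90 = 31, 121 − 87 = 34 or 121 − 85 = 36 days after the last dose for subjects maintained on 300, 200 or 100 mg BID. Each figure can shift by up to 2 + 2 = 4 days with the two visit windows. It would detect many, but not all, pregnancies arising in the 30 days after dosing.
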